Study Title: Mobile Contingency Management for Concurrent Abstinence from Cannabis and Cigarette Smoking: A Pilot Study

Clinical Trials identifier: NCT02869451

Date of Document Collation: 3/8/2018

Background

Cannabis is the most widely used illicit drug in the United States, with 19.8 million current users (Substance Abuse Mental Health Services Administration, 2014). Population-based data indicate that almost all cannabis users (90%) have a lifetime history of tobacco smoking (Agrawal, Budney, & Lynskey, 2012), and the majority (74%) currently smoke tobacco (Richter et al., 2004; Richter, Ahulwalia, Mosier, Nazir, & Ahulwalia, 2002). While cannabis use alone is associated with significant adverse health effects (Hall & Degenhardt, 2009; Hall, Degenhardt, & Lynskey, 2001), tobacco smoking is the number one preventable cause of illness and death in the U.S. (Centers for Disease Control and Prevention, 2010). This is especially true for illicit drug users, for whom the tobacco-related mortality rate is twice that of the general population (Hurt et al., 1996). Among cannabis users, smoking tobacco is associated with increased frequency of cannabis use (Richter et al., 2004), increased morbidity (Peters, Budney, & Carroll, 2012; Taylor et al., 2002), and poorer cannabis cessation outcomes (de Dios, Vaughan, Stanton, & Niaura, 2009; Gray et al., 2011). Treatment among dual users is complicated, as the cessation of one substance is often associated with increased utilization of the other (Akre, Michaud, Berchtold, & Suris, 2010; Copersino et al., 2006; Allsop et al., 2014). There is a surprising lack of research, however, focused on addressing cessation of both substances simultaneously (Agrawal et al., 2012; Peters et al., 2012; Becker, Haug, Sullivan, & Schaub, 2014). Few preliminary studies have targeted both behaviors concurrently. Preliminary studies include two small open trials (Hill et al., 2013) and a web-based intervention aimed at increased readiness to quit both substances (Becker et al., 2014). Hill and colleagues (2013) enrolled 12 adults with cannabis use disorder (CUD) and nicotine dependence in an open trial that included 10 treatment sessions. Forty-two percent of participants dropped out before the end of treatment; of those who remained, tobacco smoking was reduced (number of daily cigarettes smoked); however, no change was observed in cannabis use. Becker and colleagues (2014) demonstrated that brief web-based interventions (psychoeducation, personalized normative feedback; motivational interviewing) can increase readiness to guit tobacco and cannabis, suggesting that dual users are interested in quitting both substances, but effective treatments are not available. Thus, more intensive and innovative interventions are needed to reduce dual use of cannabis and tobacco.

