Our long-term goal is the reduction of morbidity associated with cannabis and smoking through the implementation of cost-effective, evidence-based interventions that maximize recovery. The purpose of this **pilot** project is to evaluate feasibility of treatment, recruitment, and abstinence bioverification methods for a combined cannabis and tobacco smoking tele-health mCM intervention that will effectively treat both disorders. Results from this pilot project will be used in support of an NIH grant to further develop the treatment and evaluate its feasibility and acceptability on a larger scale.

Preliminary Data

We developed and tested the mCM smoking app in combination with telephone CBT and used them in an initial validation study of 22 smokers with posttraumatic stress disorder (PTSD; Hertzberg et al., 2013). In this study, participants were randomized to 4 weeks of mCM plus CBT or to CBT plus yoked non-contingent reinforcement condition (i.e., compensation was based on earnings of participant matched from the other condition). Participant adherence to the protocol of submitting two on-time valid video readings daily was excellent (92%). Three-month self-reported 7-day point-prevalence quit rates were 18% in the yoked group and 50% in the mCM group. These preliminary results suggest that the tele-health mCM intervention is feasible and may lead to a longer duration of abstinence when CBT complements mCM in a multi-component intervention.

To further evaluate the tele-health mCM intervention, we enrolled 20 homeless smokers, and they all received the tele-health mCM intervention with CBT and standard smoking pharmacotherapy (Carpenter et al., 2015; Hertzberg et al., 2013). The majority of the sample (70%) had a history of CUD. Adherence to the timing and procedures for uploading videos with the mCM app was excellent during the treatment phase (93%). After 4 weeks of the tele-health mCM intervention, bioverified 7-day point-prevalence abstinence was 50%. Despite removing monetary compensation for abstinence at 4 weeks post-quit, bioverified abstinence in the tele-health mCM group was 55% at a 3-month follow-up assessment, and 45% at a 6-month follow-up assessment (Carpenter et al., 2015).

Methods

Participants

Up to 10 participants with CUD and smoking will be enrolled, with a goal of 5 participants completing the intervention.

Participants will be eligible for inclusion in the study if they meet the following criteria:

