application (mCM) targeting BOTH smoking and cannabis use. Treatment components are separately described herein. Table 1 provides a summary of study visits, procedures, and compensation.

Table 1. Stu	Table 1. Study Procedures						
Session	Tasks	Time	Payment				
1 (lab)	Consent	30 min	\$100				
	Screening (clinical interview, questionnaires,	3 ½ hours					
	impulsivity tasks)						
	Urine sample, breath sample taken						
	Counseling session 1						
	mCM equipment training						
2 (phone)	Counseling session 2	30 mins.	None				
3 (phone)	Counseling session 3	30 mins.	Up to \$49 for monitoring				
	Begin practice mCM for 1 week		between 3 & 4				
	Begin bupropion if using						
4 (phone)	Quit day	30 mins.	Up to \$402.50 for 2 weeks				
	Counseling session 4		monitoring between 4 & 5				
	Begin abstinence mCM						
	Begin NRT						
5 (phone;	Counseling session 5	30 mins.	Up to \$892.50 for 2 weeks				
2 wks post	Continue abstinence mCM		monitoring between 5 & 6				
session 4)	Reduce NRT to 14 mg						
	Continue use of "rescue" NRT PRN						
6 (phone;	Quick phone check-in	10 min	Up to \$98 for monitoring				
2 wks post	Continue mCM wash-out period		between 6 & 7				
session 5)	Reduce NRT to 7 mg						
	Continue use of "rescue" NRT PRN						
7 (lab; 2	Feasibility interview, question naires,	1 hour	\$35 for returned				
wks post	impulsivity tasks		equipment, \$100 for				
session 6)	Saliva sample, CO reading, and urine drug		session				
	screen Prompt to return equipment						
	Cease NRT						
8 (lab; 3	Questionnaires, impulsivity tasks	30 min	\$100				
month	Saliva samples, CO readings, and urine drug						
follow-up)	screens						
9 (lab; 6	Questionnaires, impulsivity tasks	30 min	\$100				
month	 Saliva samples, CO readings, and urine drug 						
follow-up)	screens						
	Cease bupropion						
		TOTAL	Up to \$1,877				

Measures. At the screening visit, participants will provide sociodemographic data on age, gender, education, income, ethnicity, marital and employment status. They will be interviewed using the substance use disorders section and the psychotic and associated symptoms section of the Structured Clinical Interview for DSM-5 (SCID-5; First, Williams, Karg, & Spitzer, 2015). Participants will also

complete the following measures:

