With regards to FDA device issues, Bedfont/coVita will not be seeking 510k Clearance on the iCO™ Smokerlyzer® because it does not meet the standard/criteria of a medical device. Device manufacturers are required to follow FDA guidance to inform them of when a device necessitates 510k application. Per [name] at Bedfont/coVita, their regulatory team has determined that this is not necessary primarily because they do not make a medical claim about the device, as it is not designed to diagnose a disease or illness. Simply measuring CO is not diagnosing a disease or illness and Bedfont/coVita makes no medical claim that the iCO™ Smokerlyer® can be used to screen for CO poisoning.

We will compare self-reports to objective measures of cannabis use during the abstinence period. Feasibility of using proposed methods will be based on the observed concordance of self-report, CO readings, and saliva testing in the early abstinence period. If saliva tests taken before bedtime do not coordinate with participants' self-report during early abstinence weeks 1-2, we will modify procedures for subsequent weeks in order to 1) increase frequency of monitoring and 2) have the timing less predictable; e.g., more frequent cannabis readings will occur randomly between 8am-11pm, clustered in the evenings (8pm-11pm) and weekends (Friday-Sunday) (Alessi & Petry, 2013). While potentially more burdensome, this modification will be designed to alarm-prompt readings to occur up to 14 occasions each week to ensure adequate coverage. This procedure is designed to ensure that participants do not know when they will have a long time period between readings that would provide an opportunity for using cannabis that would be metabolized before the next reading. When prompted, participants will have one hour to submit their sample, with a reminder prompt at 30 minutes. Similar procedures have produced good adherence in previous research (Alessi & Petry, 2013). At the end of the monitoring period, qualitative data will be collected assessing bio-verification preferences, barriers, and any attempts to tamper or alter samples.

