Pharmacotherapy for Smoking Cessation. Participants will receive standard pharmacotherapy for smoking cessation. Study medications will be mailed to participants after the screening visit. Study medications consist of bupropion, an 8-week course of nicotine patch use and up to two rescue methods (e.g., nicotine gum, lozenge). Participants will be screened for suitability for nicotine replacement therapy (NRT) or other smoking cessation medication, and the study physician will determine safety for NRT and bupropion use. Participants will receive tailored amount and delivery type of NRT based on number of cigarettes smoked per day using an established protocol (Bars et al., 2006). Bupropion will be prescribed to start one week prior to their quit day [150 mg/daily for days 1-7 and 300 mg/daily (administered in two daily doses) until the 6-month follow-up. If a participant with a seizure disorder, history of or current hepatitis and/or cirrhosis, renal impairment, and/or uncontrolled diabetes wishes to enroll in the study, he/she will not receive contraindicated medications. If a participant with any of these medical conditions is unwilling to participate in the study without taking bupropion, he/she will be withdrawn from the study.

Follow-Up Visits. Participants will be asked to attend three follow-up visits at end of treatment, 3- and 6-months post-quit. At the follow-up visits, participants will be asked about their experiences with various treatment components. These will include closed ended questions and open-ended interview

questions. In addition, the study coordinator will ask questions about alliance with the study therapist. Participants will be asked to complete symptom self-report measures and computerized impulsivity tasks at each follow-up visit. Participants will be asked about smoking and cannabis use in the period since the quit date. Self-reported abstinence will be bioverified by several means. Self-reported prolonged abstinence from cannabis use will be verified by urine and OF cannabis assessments. Self-reported abstinence from smoking will be verified by saliva cotinine assay and CO reading.

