Participants will be offered NRT, and there are risks associated with the use of NRT. Minimal risks associated with wearing a nicotine patch include skin irritation, dizziness, lightheadedness, increased heart rate or blood pressure, nausea or vomiting. If a participant indicates a contraindication to NRT (e.g. uncontrolled hypertension), medical clearance for NRT will be sought from the participant's primary care physician and/or the study physician. If a participant with a seizure disorder, history of or current hepatitis and/or cirrhosis, renal impairment, and/or uncontrolled diabetes wishes to enroll in the study, he/she will not receive contraindicated medications.

Participants who are medically eligible will also be prescribed bupropion SR. Risks of bupropion use include dry mouth, insomnia, nausea, constipation, headache, shakiness or jitteriness, skin rash, sweating, allergic reaction, change in appetite, weight loss, dizziness, tremor, thinking abnormally, hot flashes, worsening depression or suicidal thoughts and behavior, and ringing in the ears. At the highest dosage of bupropion to be used in this study, seizures occurred in 1 out of every 1000 (0.1%) who took this drug. Participants are informed that they are not required to take bupropion, and will be allowed to participate in the study if they refuse to do so.

There is a potential risk associated with the loss of confidentiality of study data. Specifically, collection and transfer of videotaped carbon-monoxide monitoring have risks with regards to privacy and confidentiality. Please see "Protection From Risk: Data Security" for details on reduction of risk with regards to the proposed videotaping.

Protection From Risk: Data Security

While participants may benefit from quitting smoking and marijuana use, there are no guaranteed benefits to the individual participant and no immediate benefits of the proposed research to others. There are potential benefits to others from the information generated that potentially will be helpful in developing new combined treatments for smoking and marijuana use. In our opinion, the anticipated benefits of this study outweigh the potential risks. The study is completely voluntary and participants are informed that they are free to refuse to answer any items on the questionnaires or questions from the interview. They are also informed that they are free to decline participation in procedures and can withdraw from the study at any time.

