semi-parametric methods (e.g. quasi-likelihood methods; McCullagh & Nelder, 1989). In planning a full RCT of the tele-health mCM intervention for CUD and smoking, it is important to evaluate study feasibility and treatment procedures, as well as gaining information about effects on proposed outcome variables. To remain consistent with guidelines for designing and evaluating pilot studies, analyses will be primarily descriptive (Thabane et al., 2010) and aimed at informing feasibility and needed modifications rather than detecting statistically significant between-group differences (Leon, Davis, & Kraemer, 2011). However, to best utilize participant data to optimally design the treatment, we have established several objectives to indicate whether the planned trial is feasible.

Feasibility of cannabis abstinence assessment will be based on data from this pilot. While the validity of the Alere Oratect Oral Fluid Drug Screen Device has demonstrated excellent agreement with clinical samples analyzed with GC/MS methods, the utility of using daily saliva tests and CO (which measures carbon monoxide for cannabis smoking in the past 3 hours) has not been evaluated. We will examine the utility of the proposed saliva testing protocol. Additionally, qualitative data on the use of saliva tests will be examined to ensure that participants find it acceptable and preferable to in-clinic assessment methods.

The feasibility and acceptability of the multi-component tele-health mCM intervention will be assessed. We will collect frequency data regarding the number of videos transmitted, number of study measures completed at each time point, the amount of missing data (including missed videos), the number of sessions attended, and the frequency and severity of adverse events. We will assess the association of potential stratification variables (sociodemographic, psychiatric, and CUD/smoking severity variables) with feasibility indices, adherence to study protocol (video transmission, completion of study measures at each time point, session attendance), attrition, and adverse events. We will also determine whether attrition rates and frequency and severity of adverse events exceed those of previous smoking treatment trials. These data will provide important information useful in refining the intervention and associated assessments/procedures prior to their implementation in a larger-scale RCT.

References

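### No exit contact is described for participants who stop early, so the participant-reported view of saliva testing may come only from those who return to the clinic

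*Combined protocol and SAP*

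**What the plan says.** The timing of participant-reported data is set in three places.

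- **mCM Procedures:** "At the end of the monitoring period, qualitative data will be collected assessing bio-verification preferences, barriers, and any attempts to tamper or alter samples".
- **Table 1:** the entry "Feasibility interview" appears once, at session 7 (lab). The phone contacts, sessions 2 to 6, list no acceptability item.
- **Follow-Up Visits:** "Participants will be asked to attend three follow-up visits at end of treatment, 3- and 6-months post-quit", and "At the follow-up visits, participants will be asked about their experiences with various treatment components". In Table 1 the only lab visits after screening are sessions 7, 8 and 9.

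The Data Analyses section, which appears twice in the document with the same text, gives these data a specific job: "qualitative data on the use of saliva tests will be examined to ensure that participants find it acceptable and preferable to in-clinic assessment methods". It also says that feasibility and acceptability of the whole intervention will be assessed. In the same paragraph it lists counts of videos, missing data, measures completed, sessions attended and adverse events, and analyses of adherence and attrition.

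The plan foresees that some participants will not finish. The Participants section says: "Up to 10 participants with CUD and smoking will be enrolled, with a goal of 5 participants completing the intervention". Under Protection From Risk: Data Security, "They are also informed that they are free to decline participation in procedures and can withdraw from the study at any time". No section describes an exit interview, or a record of the reason, when someone stops mCM or withdraws.

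**The concern.** Finding out whether this treatment and this way of verifying abstinence are feasible is the purpose of the pilot, and its results are meant to shape a larger trial. A participant who gives up because filming saliva and CO tests twice a day is too much trouble knows something the team needs. Under the schedule as written, that person is asked about it only by coming to a later lab visit. If they do not come, their reason for stopping is not among the data the plan sets out to collect.

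The comparison with in-clinic testing is the most exposed. Attending a clinic is the burden that home testing is meant to remove, yet the preference is asked for at a clinic visit. If those who return differ from those who do not, the pilot could carry a distorted picture of acceptability, and no account of barriers, into the next trial.

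**Working it through.** **1. When is each kind of data collected?**

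| Source | Timing | Covers someone who stops and does not return? | Shows why they stopped? |
|---|---|---|---|
| Preferences, barriers, tampering (mCM Procedures) | End of monitoring | No | Not collected |
| Feasibility interview (Table 1) | Session 7, lab | No | Not collected |
| Questions on treatment experience (Follow-Up Visits) | End of treatment, 3 and 6 months | No | Not collected |
| Daily diary (mCM Procedures) | Each evening of monitoring | Until they stop | No; cigarette and cannabis use only |
| Process counts, attrition (Data Analyses) | Throughout | Yes | No; shows that they stopped |
| Toll-free line, weekly staff meetings (Data and Safety Monitoring Plan) | Throughout | Possibly | Possibly, but not described as acceptability data |

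Session 7 falls 2 + 2 + 2 = 6 weeks after quit day (session 4 to 5, 5 to 6, 6 to 7 in Table 1).

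**2. Is there a planned figure to reproduce?** No. The plan gives up to 10 enrolled and a goal of 5 completing, with no retention assumption, no precision target and no defined acceptability proportion. The implied completion is 5/10 = 50%, but 10 is a ceiling and 5 is a goal for completing the intervention. Neither is an attendance figure for session 7.

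**3. What could non-attendance do? (illustration)** Let N be the number enrolled, m the number interviewed and x the number of those who approve. With nothing known about the other N − m, approval among all enrolled lies between x/N and (x + N − m)/N.

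- m = 5, x = 5, N = 10: observed 5/5 = 100%. Bounds 5/10 = 50% to (5 + 5)/10 = 100%.
- m = 5, x = 4, N = 10: observed 4/5 = 80%. Bounds 4/10 = 40% to (4 + 5)/10 = 90%.
- m = 8, x = 8, N = 10: observed 8/8 = 100%. Bounds 8/10 = 80% to (8 + 2)/10 = 100%.

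The values of m and x are assumed. In the first case the exact 95% interval for the observed proportion is already wide: the lower limit is 0.025^(1/5) = 0.478, so 48% to 100%. The bounds show a separate uncertainty, due to who was asked.

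**4. How large a bias, under assumptions?** If a fraction r is interviewed, with approval p_s among them and p_l among the rest, the interviewed group overstates the all-enrolled rate by (1 − r)(p_s − p_l). Assume p_s = 0.9 and p_l from 0.5 down to 0.1:

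- r = 0.50: 0.50 × 0.4 = 0.20 to 0.50 × 0.8 = 0.40, or 20 to 40 points.
- r = 0.58: 0.42 × 0.4 = 0.168 to 0.42 × 0.8 = 0.336, or 17 to 34 points.
- r = 0.80: 0.20 × 0.4 = 0.08 to 0.20 × 0.8 = 0.16, or 8 to 16 points.
- If p_l = 0.9, the bias is zero at every r.

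The r = 0.58 row uses the dropout that the Background section cites for a 12-person open trial in dual users: "Forty-two percent of participants dropped out before the end of treatment". On 10 enrolled that would be 0.42 × 10 = 4.2, about 4 people. Treating dropout there as missing the interview here is an assumption.

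**The case against.** The other side has a good deal to say.

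- **Early stoppers are not excluded.** A reader might infer that the timing rule by itself selects completers. The documents do not support that. Nothing limits sessions 7 to 9 to those who finished monitoring, and each visit pays $100. Someone who stops mCM in the first week is still due at session 7 and can be asked about their experience at two later visits. The data are lost only when a person withdraws altogether or misses every visit. This stands, and it limits the point.
- **Acceptability does not rest on interviews alone.** A reader might infer that the whole acceptability conclusion depends on those who stayed. It does not. Data Analyses also assesses the intervention through counts that include early stoppers, and mCM Procedures judges the testing method by agreement between self-report, CO and saliva. The point is therefore confined to participant-reported acceptability, preferences and barriers. Within that scope the counts are no substitute, because they carry no reasons.
- **No acceptability percentage is a planned output.** The data are qualitative, and the percentages above are illustrations. The bounds show uncertainty, not upward bias. A reader might take overstatement as established, but the direction is plausible and unproven.
- **Attrition may be low.** Preliminary Data reports 92% and 93% adherence to video monitoring, and the cited open trial is not described as using contingency management. However, those two studies were of smoking. The filmed saliva test is new in this study, and Background says its feasibility for contingency management of cannabis use disorder is untested.
- **Staff may hear the reasons anyway.** The phone sessions, toll-free line and weekly meetings make this possible. The line and the meetings belong to safety monitoring, and nothing says that what is heard will be recorded or analysed as acceptability data.
- **The end of monitoring is not defined for someone who stops early.** A per-participant reading is open, but Table 1 places the interview only at session 7, so the text needs to say so if that is meant.

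**Conclusion.** The point holds in a limited form. Participant-reported acceptability, preference and barrier data are scheduled only at the end of monitoring and at later lab visits, and no exit contact is described. Those who stop or withdraw and also miss sessions 7 to 9 give none. The participant-reported finding on saliva testing would then rest on those who return, and reasons for stopping would be lost.

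The size cannot be fixed from the documents, because no session 7 attendance rate is stated. If 5 of 10 were interviewed and all 5 approved, the value for all 10 could be 50% to 100%. An overstatement of 20 to 40 points at half attendance needs the further assumption that approval is 90% among those interviewed and 10% to 50% among the rest. With equal approval there would be no bias.

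This is a cheap improvement to a descriptive pilot. It does not undermine the design.

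**What to change.** Amend mCM Procedures, Follow-Up Visits and Table 1 so that the existing feasibility interview is due at the end of monitoring or when the participant stops mCM or withdraws, whichever is first. For those who stop early, give it by telephone, with their consent, and record the main reason for stopping. In both copies of Data Analyses, state that acceptability and barriers will be reported against all enrolled, with completers and early stoppers shown separately and the number not reached given.

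The cost is a minor amendment and a few calls by existing staff: about five if 10 enrol and 5 complete. Counselling is already given mainly by phone. Some stoppers will not answer, and stoppers will be interviewed at a different time from completers, which the report should say.

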Standard cut-points of 10 ng/ml for cotinine and 50 ng/ml for THC9-carboxylic acid (THC-COOH) will be used to determine abstinence from nicotine and marijuana, respectively. Self-reported and bioverified prolonged abstinence from marijuana, tobacco smoking and dual abstinence at the 6-month follow-up will be the primary end-point. Secondary cannabis use and tobacco smoking outcomes will include 7-and 30-day point prevalence abstinence at each assessment, in which abstinence is defined as no cannabis or tobacco use in the prior 7 or 30 days, respectively. Outcomes will also include cannabis consumption patterns such as standard joints/week and proportion of days abstinent. Participants will also report number of cigarettes smoked each day and days of smoking abstinence. Collection of cannabis and tobacco smoking use data will allow for calculation of dual abstinence days and longest duration of dual abstinence.

Participant Reimbursement. Based on our experience in our previous clinical trials, we are including \$100 compensation for completing baseline, end of treatment, and 3- and 6-month follow-up assessments (up to \$400). To ensure that participants return the CO monitor and phone, we are providing postage-paid return mailers and adding a \$35 incentive for equipment return. Participants can earn up to \$1,442for full participation and abstinence for the mCM portion of the study. Total possible payment for participation is \$1,877.

Potential Risks

There is a risk of discomfort or distress in answering questions on the study measures. However, distress and discomfort related to questionnaire completion is usually temporary and well-tolerated. Risks also include discomfort related to quitting marijuana and quitting smoking. Symptoms of marijuana withdrawal may include headache, insomnia, sweating, night sweats, anxiety and/or depression, nightmares or vivid dreams, irritability, and cravings for use. Quitting smoking may cause difficulty concentrating, poor sleep, increased appetite, anxious or depressed mood, and craving for cigarettes.

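### At the end-of-treatment visit, the 10 ng/ml cotinine cut-point, applied as the plan implies, can fail tobacco quitters who are still using study-supplied NRT

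*Combined protocol and SAP*

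**What the plan says.** All of the following is in the combined protocol and SAP.

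- **Visits.** Follow-Up Visits: "Participants will be asked to attend three follow-up visits at end of treatment, 3- and 6-months post-quit".
- **Verification of smoking abstinence.** Same section: "Self-reported abstinence from smoking will be verified by saliva cotinine assay and CO reading". No visit is exempted.
- **Cut-points.** Same section: "Standard cut-points of 10 ng/ml for cotinine and 50 ng/ml for THC9-carboxylic acid (THC-COOH) will be used to determine abstinence from nicotine and marijuana".
- **Outcomes.** The primary end-point is stated as "Self-reported and bioverified prolonged abstinence from marijuana, tobacco smoking and dual abstinence at the 6-month follow-up will be the primary end-point". The secondary outcomes are "7-and 30-day point prevalence abstinence at each assessment". The plan then defines them by use of the substances, not by nicotine: "in which abstinence is defined as no cannabis or tobacco use in the prior 7 or 30 days".
- **Study-supplied nicotine.** Pharmacotherapy for Smoking Cessation provides an 8-week patch course and up to two rescue methods. Table 1 starts NRT on quit day (session 4), reduces it at sessions 5 and 6, and lists stopping NRT as a task of session 7.
- **Samples.** Table 1 lists "Saliva sample, CO reading, and urine drug" screen at session 7, and "Saliva samples, CO readings, and urine drug" screens at sessions 8 and 9.

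Cotinine is mentioned only in Follow-Up Visits. Nothing there or elsewhere says how an NRT user, or a participant who fails cotinine but passes CO, is to be classified.

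**The concern.** The cut-point is described as a test for nicotine, whereas the outcome is tobacco use. The two coincide only in people who take no nicotine from another source, and this study hands out such a source. At the one follow-up visit to which NRT is still scheduled, a cotinine result above the cut-point cannot tell a smoker from a quitter on NRT.

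At stake are the end-of-treatment 7- and 30-day tobacco abstinence rates and any dual abstinence rate built on them. For quitters on NRT the error runs in one direction, towards too low a rate. The pilot is meant to inform a grant application and a larger trial, so an outcome rule that is carried forward unsettled would cause the same problem there.

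**Working it through.** The plan gives no figure that depends on this rule, so there is none to reproduce. The check is of timing, of the conditions the point needs, and of what can be said about size.

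**1. Is NRT scheduled when the sample is taken?** From Table 1, counting from quit day:

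- session 4 = week 0 (NRT begins)
- session 5 = 0 + 2 = week 2
- session 6 = 2 + 2 = week 4
- session 7 = 4 + 2 = week 6 (NRT stops; saliva is taken at the same visit)

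If the 8-week patch course ran from quit day, 8 − 6 = 2 weeks would remain at session 7. On either schedule, NRT runs up to the sampling visit.

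**2. Are the later visits exposed?** Taking 3 and 6 months as about 13 and 26 weeks, scheduled NRT has been over for:

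- 13 − 8 = 5 to 13 − 6 = 7 weeks at 3 months
- 26 − 8 = 18 to 26 − 6 = 20 weeks at 6 months

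If NRT stops on schedule, the problem is confined to session 7.

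**3. What must hold for a quitter to be misclassified?**

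- *Cotinine is assayed at session 7.* Follow-Up Visits counts end of treatment among its three visits and exempts none. Table 1 does not say what the session 7 saliva is for. Its wording is singular there and plural at sessions 8 and 9, which might mean that a cotinine sample is added later. But CO readings and drug screens also turn plural at those sessions, so this is not decisive.
- *The secondary outcomes are bioverified.* Follow-Up Visits says in general terms that self-reported abstinence will be bioverified, and its smoking sentence is not limited to prolonged abstinence. The outcome definitions use the word bioverified only for the primary end-point.
- *Both markers must pass.* The plan joins cotinine and CO with *and*, but gives no rule for discordant results.

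**4. Size.** Let u be the share of true quitters using NRT at session 7, and p the share of those at or above 10 ng/ml because of it. If all three conditions hold:

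verified rate ÷ true rate = 1 − u × p

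The documents give neither u nor p. With both assumed to lie anywhere from 0 to 1, the ratio runs from 1 (no bias) to 0, so it sets the direction and nothing more. What is fixed is the effect of one misclassified person, taking the plan's goal of 5 completers and maximum of 10 enrolled:

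- 1/5 = 20 percentage points
- 1/10 = 10 percentage points

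**The case against.** The strongest reply is that the argument rests on three unsettled readings. Session 7 saliva may be for THC only: the screening visit uses a saliva sample for cannabis alone, and Table 1 names no cotinine assay at any visit. The secondary outcomes may rest on self-report, since only the primary end-point is called bioverified where the outcomes are defined. A CO pass might also be allowed to stand against a cotinine failure. If any one of these readings is right, there is no bias. This stands, and the point is therefore conditional. It does not remove the gap, because the more natural reading of Follow-Up Visits goes the other way on all three and the plan does not settle any of them.

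It is also fair to say that NRT has been stepped down by session 7, that uptake is unknown (Potential Risks says only that NRT is offered), and that this is a single-group pilot of 5 to 10 people with mainly descriptive analyses. No stated decision rule uses end-of-treatment tobacco abstinence. All of this stands and keeps the point minor. It does not make the rule sound: with so few people, a single misclassification visibly changes a descriptive rate.

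CO is collected at session 7 and is not a nicotine marker. That makes a remedy easy, but the plan does not say that CO overrides cotinine, so it does not close the gap as written.

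**Conclusion.** The concern holds in conditional form and is minor. If cotinine is assayed at session 7, the secondary abstinence outcomes are bioverified and both markers must pass, a true tobacco quitter using study-supplied NRT can be counted as not abstinent. End-of-treatment tobacco and dual point-prevalence abstinence would then be biased downward by an unknown amount, at 20 points per misclassified person with 5 participants or 10 points with 10.

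A reader might infer two stronger things that the documents do not support:

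- *That the primary end-point is compromised.* It is set at 6 months, well after scheduled NRT ends. It is affected only if prolonged abstinence also requires a cotinine pass at session 7, which the plan does not state. This assumes that NRT has stopped as scheduled.
- *That the end-of-treatment rate would collapse among NRT users.* The documents give neither NRT uptake nor cotinine levels on NRT, so no particular loss can be claimed.

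**What to change.** In Follow-Up Visits:

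- State whether session 7 saliva is assayed for cotinine. If it is for THC only, say so; no further change is then needed on this point.
- If it is assayed, state whether the 7- and 30-day outcomes are bioverified and how discordant cotinine and CO results are classified.
- Record current NRT use at session 7. For participants reporting recent use (window stated in advance), verify self-reported tobacco abstinence by the visit CO against a cut-point fixed in advance, rather than failing them on cotinine. The plan's own < 6 ppm, at present a payment criterion, is one candidate.
- Report cotinine and CO results separately at that visit.
- Keep cotinine plus CO at 3 and 6 months, and state that prolonged abstinence does not depend on a session 7 cotinine pass.

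The cost is one question, a few sentences and an extra results line; CO is already collected at the visit. The downside should be stated as a limitation. CO has a short detection window, and the Background notes that smoked cannabis raises it too. Verification in NRT users at session 7 is therefore less sensitive and less specific for tobacco, and a participant on NRT who still smokes could pass.

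Separately, the NRT duration in Table 1 (stops at week 6) and in Pharmacotherapy for Smoking Cessation (8-week course) should be reconciled. The conclusion here is the same on either.
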